1. OBJECTIVES

Our primary objective is to determine if MSC treatment, in neonates with PAIS, is safe in the acute setting, including vital signs at time of treatment, blood sampling before and after MSC treatment and occurrence of any adverse events or toxicity. Secondly we will investigate safety of MSC treatment at 3 months, in terms of SAEs and tumorigenicity on MRI.

Primary Objective

• To determine if MSC treatment in (near-)term infants with PAIS is safe in the acute setting.

Safety is defined primarily as the absence of treatment-related serious adverse events (SAEs) according to the Consolidated Standards of Reporting Trials (chapter 7.2), secondly as the absence of dose-limiting toxicity, defined as death within 24 hours after MSC transplantation or anaphylactic shock related to the MSC administration. At least, all patients will be regularly and intensively assessed, including vital signs, before and 24 hours after treatment, until discharge from our hospital. Also, blood sampling will be performed before and 24 hours after treatment with MSCs to determine infection and inflammation parameters. Acute safety will be determined until discharge.

Secondary Objectives

- To determine if MSC treatment in (near-)term infants with PAIS is safe in the subacute setting.
 - Subacute safety is defined primarily as the absence of treatment-related serious adverse events (SAEs) according to the Consolidated Standards of Reporting Trials (chapter 7.2) until the age of 3 months. Patients will then be asked to report on other SAEs, including infections.
- To determine if MSC treatment in (near-)term infants with PAIS is safe at 3 months in terms of cerebral tumorigenicity.
 - To assess safety of MSC treatment on the brain, infants will be scanned using MRI prior to MSC treatment and at 3 months of age. Long-term adverse effects on the brain in terms of tumorigenicity will be determined using this MRI, which is part of regular stroke follow-up program.

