AEs and SAEs occurring during the study will be recorded in the manner described under Section 7.2. All SAEs will be followed up until resolution or until the event is considered stable. SAEs resulting in a life threatening condition or death will be reported to the regulatory authorities and the EC in line with the local regulatory requirements. In addition the investigator will report any SAEs resulting in death and/or a life-threatening situation and any unexpected related SAEs to the regulatory authorities and the Ethics Committee (EC) in line with the local regulatory requirements. An independent data safety and monitoring board (DSMB) has, in addition to an internal safety review committee, been established to carry out further safety surveillance (see Paragraphs 7.2.3 and 7.4).

[figure not shown]
MRI measurements

For secondary parameters, subjects will be scanned on a 3 Tesla MR scanner as soon as possible after clinical suspicion of PAIS and again 3 months after the MSC treatment. Further details on MRI measurements can be found in chapter 6. All infants will return to the WKZ, UMCU for a MRI scan at 3 months of age.

Follow-up

After the intervention period, subjects will be followed until 3 months corrected age. At 3 months neurological assessment will be performed as part of the regular stroke follow-up program. This will also include filming spontaneous and endogenous movements (General Movements). Additionally, fidgety movements will be assessed. Neuromotor development will also be assessed using the HINE. After parental consent, results from these examinations will be used for this study. Subjects in this study will also be followed for at least 2 years of age at regular time points. This follow-up is part of regular care for neonates with PAIS, but these results are not part of this study protocol and are beyond the scope of this study.

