6.1.2 Secondary study parameters/endpoints

To determine if MSC treatment in (near-)term infants with PAIS is safe in the subacute setting, patients will be monitored until the age of 3 months. Subacute safety is defined primarily as the absence of treatment-related serious adverse events (SAEs) according to the Consolidated Standards of Reporting Trials (chapter 7.2) until the age of 3 months. Patients will then be asked to report on other SAEs, including infections, during the first three months of age. Whenever their child experiences fever, or other signs of infection/inflammation, there will be tested for bactermia, systemic infections and/or post-administration virus infections.

To determine if MSC treatment in (near-)term infants with PAIS is safe at 3 months in terms of cerebral tumorigenicity, infants will be scanned using MRI prior to MSC treatment and at 3 months of age. Long-term adverse effects on the brain in terms of tumorigenicity will be determined using this MRI, which is part of regular stroke follow-up program. Scans will be assessed by a pediatric radiologist to see if there are any adverse events on the brain (including tumor formation).

All MRI investigations will be performed on a 3.0 Tesla MR system. Infants will be sedated with a combination of chlorpromazine (0.5 mg/kg), pethidine (2 mg/kg), and promethazine (0.5 mg/kg) intramuscularly, which is part of our standard MRI procedure. During MR

examination the neonates will be placed in a vacuum fixation pillow (Med Vac Infant Immobilizer Bag, Radstadt, Austria) to prevent movement. Monitoring will be performed using pulse oximetry (Nonin, Minneapolis, MN) and respiration rate will be observed using the standard Philips equipment (Philips Medical Systems, Best, Netherlands). For hearing protection we will use: Minimuffs® (Natus Medical Incorporated, San Carlos, CA, USA), Earmuffs (EM's 4 Kids, Brisbane, Australia) and a passive acoustic noise dampener, the acoustic hood that properly fitted in the bore of the MRI scanner (Intera, Philips Medical, Best, Holland).

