7.4 Follow-up of adverse events

All AEs will be followed until they have abated, or until a stable situation has been reached. Depending on the event, follow up may require additional tests or medical procedures as indicated, and/or referral to the general physician or a medical specialist. SAEs need to be reported until discharge after the second MRI around the age of 3 months. As described in chapter 7 of the IB, MSCs do not survive for a very long period. When MSCs disappear within a short time frame and they are no longer present in the subject, they are not able/unlikely to lead to (serious) adverse events such as death, tumor formation or disturbances of the immune system. We have therefore decided that after a period of 3 months, AE or SAEs are very unlikely to be linked to the use of MSCs and conclusions regarding safety of MSCs can be drawn.

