Planned actions: If a patient develops a new viral infection that is suspected to be due to transfusion of blood products or intranasal administration of the investigational product, a look-back procedure should be initiated by the treating physician according to local regulations for all blood products received. If an MSC donor is proven to be the source of virus infection, this shall be considered a serious adverse event.

3. Long-term adverse effects: Ectopic tissue formation and tumorigenicity Planned actions: If ectopic tissue formation or a new malignancy is detected in a patient at any time following infusion of the investigational product, information regarding the MSC donor's HLA-typing will be provided so that genetic testing for presence of donor-derived MSC can be performed. If MSC donor-derived tissue is present either as malignant tissue or in the malignancy surrounding tissue, this is regarded as a serious adverse reaction. Treatment will be accordingly to the malignant tissue.

The extra burden of the present study for the included infants is considered to be very limited to non-existent given the fact that besides the nasal treatment to apply the MSCs, treatment is not different compared to the standard acting treatment protocol for newborns with PAIS.

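### A single 3-month MRI cannot support the long-term tumorigenicity label, and SAE reporting stops at that scan while malignancy is to be acted on at any time

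*Combined protocol and SAP*

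**What the plan says.** The secondary objective in section 1 asks whether treatment "is safe at 3 months in terms of cerebral tumorigenicity". The explanatory text beneath it goes further: "Long-term adverse effects on the brain in terms of tumorigenicity will be determined using this MRI". Section 6.1.2 repeats that sentence, and the Summary places both subacute and long-term safety at the 3-month point. There is one scan before treatment and one after it, and section 2.2 caps each infant's participation at 3 months.

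On later follow-up, section 2.4 states: "Subjects in this study will also be followed for at least 2 years of age at regular time points". It describes this as regular care and adds that "these results are not part of this study protocol and are beyond the scope of this study".

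On reporting, section 7.4 states: "SAEs need to be reported until discharge after the second MRI around the age of 3 months". Its reason is that the cells do not survive long, so later events are judged very unlikely to be linked to them. Section 11.2 sets no such limit: "If ectopic tissue formation or a new malignancy is detected in a patient at any time following infusion", donor typing is to be supplied so that donor-derived cells can be sought. If they are found, 11.1e classes the event as a suspected unexpected serious adverse reaction and 11.2 as a serious adverse reaction. Section 6.7 lists malignancy among the possibly related effects that count toward stopping when seen in three patients. Section 8.1 includes tumour growth among the SAEs to be given as percentages and described qualitatively.

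**The concern.** Two things do not fit together.

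The first is the label. The objective is bounded at 3 months, but three places attach long-term to the same scan. Whoever writes the final report could draw on either wording, and only one of them is something the trial observes.

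The second is the reporting window. Tumour formation is the risk the protocol itself files under long-term effects, yet SAE capture closes for each infant at about 3 months. A malignancy found afterwards has a handling procedure but no clear path into the SAE tally or to the DSMB. Recruitment takes 12 to 24 months, so this can happen while other infants are still being treated.

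**Working it through.** **Step 1. The time limits side by side.**

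| Place | What it covers | Time limit |
|---|---|---|
| 1, secondary objective | cerebral tumorigenicity | 3 months |
| 1 and 6.1.2, explanatory sentence | long-term brain effects | the 3-month MRI |
| Summary | subacute and long-term safety | 3 months |
| 5.4, mouse evidence | neoplasia after treatment | 14 months |
| 5.4, cited human studies | long-term effects including tumours | 2 months to 4 years |
| 7.4 | SAE reporting | discharge after second MRI |
| 11.1e and 11.2 | action on malignancy or ectopic tissue | none |
| 6.7 | malignancy in the stopping rule | none stated |

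The protocol's own long-term evidence mostly runs beyond 3 months, although the shortest cited human follow-up (2 months) is below it.

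**Step 2. What a clean result would say at 3 months.** The plan gives no tumour rate, interval or power to reproduce; section 3.4 rests the sample size of 10 largely on feasibility. With zero events in n infants, the exact upper limit solves (1 − p)^n = a, so p = 1 − a^(1/n).

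- n = 10, two-sided 95% (a = 0.025): 1 − 0.025^(1/10) = 30.8%.
- n = 10, one-sided 95% (a = 0.05): 1 − 0.05^(1/10) = 25.9%.
- If only 9 or 8 infants are scanned, the two-sided limit is 33.6% or 36.9%.

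**Step 3. What it would say beyond 3 months.** Let f be the share of tumours arising by 2 years that are already visible at 3 months. The documents do not give f, so the values below are assumptions. The one-sided bound on 2-year risk is 25.9% / f.

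- f = 1: 25.9%.
- f = 0.50: 51.8%.
- f = 0.25: 25.9% / 0.25 exceeds 100%, so there is no bound.

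The scan limits later risk only through an assumption about f, which the trial does not measure.

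**Step 4. Overlap of closed reporting with ongoing treatment.** Under 6.7 the study continues only once the first three infants have had their second MRI. That is the visit at which 7.4 ends SAE reporting for them. So 10 − 3 = 7 infants would be treated after SAE reporting on the first three has closed. If recruitment lasts 12 to 24 months, the first infant is outside the reporting window for roughly 12 − 3 = 9 to 24 − 3 = 21 months of it.

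**Step 5. One case traced through the text.** Suppose a malignancy is found in an early infant at 9 months of age (illustrative). Under 7.4 it need not be reported as an SAE. Under 11.1e the coordinating investigator is contacted and donor testing can follow. If the tissue proves donor-derived, 11.1e makes it a SUSAR, and 7.2.3 provides expedited reporting to the ethics committee. If it is not donor-derived, or testing is pending, no section brings it into the SAE percentages of 8.1 or to the DSMB, although 6.7 counts possibly related malignancy without requiring donor origin.

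**The case against.** The strongest reply is that 3 months is a reasoned limit. Section 7.4 argues that cells which have gone cannot cause later harm, and the Introduction and 5.5.1 cite animal findings that few are detectable in the brain after 3 days. The fuller evidence is in the Investigator's Brochure, which is not among these documents. This stands as a rationale for where to stop. It does not turn a 3-month scan into a long-term observation, and 5.4 itself warns that a first intranasal use in humans may carry unknown risks.

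Four stronger readings are tempting, and the documents do not support them.

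- *A clean scan will be reported as proof of long-term safety.* The objective says 3 months, the Summary states the time point, the Introduction claims only first evidence of safety, and 8.1 is descriptive.
- *Two-year tumour data already exist and are being discarded.* Section 2.4 describes regular-care visits. It does not say that they include MRI or systematic recording of malignancy.
- *A late tumour is ignored altogether.* Sections 11.1e, 11.2 and 7.2.3 give donor-derived tissue a route. The gap is the remainder, plus the SAE tally and the DSMB.
- *Longer follow-up would settle the question.* With 10 infants and no events, the per-infant upper limit stays at 30.8% whatever the duration. Longer follow-up changes the period covered, not the precision.

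**Conclusion.** The point holds as a conflict of wording and of reporting rules. The objective is correctly bounded at 3 months; the long-term label in the Summary, section 1 and section 6.1.2 is not supported by the single scan to which it refers. The most a clean result can state is 0 of 10 with a two-sided 95% upper limit of 30.8% for tumour visible at 3 months, assuming all 10 are scanned and read.

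Sections 7.4, 11.1e, 11.2 and 6.7 also disagree on whether a malignancy found after 3 months is a reportable event. On the plain reading of 6.7 this affects information available while 7 of the 10 infants are treated. How likely such an event is cannot be derived from the documents. Neither part bears on the sample size or on keeping the main read-out at 3 months.

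**What to change.** 1. Delete the long-term label in the Summary, section 1 and section 6.1.2, and state the endpoint as tumour or ectopic tissue visible on MRI at 3 months.
2. In 8.1, report it as number affected over number scanned, with an exact 95% interval.
3. Reconcile 7.4 with 11.1e, 11.2 and 6.7 so that a malignancy or ectopic tissue that becomes known after an infant's 3-month MRI is still reported as an SAE and reaches the DSMB, at least until the study ends. Use one classification for donor-derived tissue in 11.1e and 11.2, and state how events found after 3 months relate to 6.7.

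Items 1 and 2 are wording only. Item 3 needs a protocol amendment, possibly substantial under 10.3, and perhaps a line in the consent form. No infant, visit or scan is added.

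Optional: with consent, a descriptive 2-year clinical safety extract from regular care (death, malignancy, ectopic tissue). This is a trade-off. Counting from first inclusion, the last infant's data would arrive at about 12 + 24 = 36 to 24 + 24 = 48 months, against an expected study length of about 2.5 years (30 months) in 2.2. It would need tracking of the infants, and it may capture only clinically apparent events.

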2. STUDY DESIGN

2.1 Description

We will perform a single-center, open-label intervention study in the NICU of the Wilhelmina Children's Hospital (WKZ) / University Medical Center in Utrecht (UMCU), the Netherlands to investigate the feasibility and safety of neonatal treatment with allogeneic MSCs in (near-) term neonates with PAIS. Since this is a phase 1/2 safety/feasibility pilot clinical trial, we will assess occurrence of adverse events.

2.2 Duration

The duration of the study for each subject from inclusion until study end will be a maximum of 3 months, comprising a 1 week intervention period and follow-up until 3 months. Subject recruitment will be (approximately) 12-24 months, at the longest, depending on when the intended number of subjects is included. This study is expected to last for approximately 2.5 years, but will only end after all 10 subjects have been included, treated and have been seen for follow-up (MRI and neurodevelopmental testing) at 3 months of age.

2.3 Setting

This study will be executed in the NICU of the WKZ/UMCU, the Netherlands, where (near-) term infants suspected of PAIS following parental consent for the study are admitted. Infants of the other participating hospitals suspected of having PAIS will be transferred to the UMCU for further diagnostic procedures (MRI) and subsequent treatment.

2.4 Study Procedures

Recruitment and inclusion

The NICU of the WKZ is known to have most expertise in neonatal stroke. Therefore, infants suspected of having PAIS will be transferred from hospitals in our region of care and also from other hospitals outside our region, to the UMCU and admitted to our NICU, allowing infants to be part of this study. Patients are eligible for our study if they meet our in- and exclusion criteria, PAIS may have been suspected with cranial ultrasound and will be confirmed within 7 days after onset of symptoms by MRI (including 3D-T1, T2 weighted, diffusion weighted imaging [DWI] and DTI sequences) and this PAIS is characterized by a predominantly unilateral ischemic lesion within the territory of the MCA, with involvement of the corticospinal tracts, cortex, white matter and basal ganglia. Following written parental consent, patients will then be included in our study. Parental consent will be obtained as soon as possible after admission at our NICU. Patients with PAIS that are diagnosed more than one week after birth are not eligible for enrolment.

Intervention period

After inclusion in our study, patients will receive MSCs as soon as possible after confirmation of the MCA-stroke, but within the first week of onset of presenting clinical symptoms. Steps to be undertaken before MSC administration include:

- A bacterial culture taken from both nostrils before administration of MSCs.
 Blood samples will be collected before administration of MSCs. Blood samples are taken routinely in the hospital for clinical purposes, but some extra material (0.5-1 mL) will be collected to determine infection markers CRP, procalcitonin and complete blood count. These samples will be combined with routine blood sampling and taken from routinely placed (arterial) catheters.
- 30 minutes prior to delivery of the MSCs, the nose will be cleaned with saline using standard procedures operative at the NICU.

After these procedures have been performed, infants will receive one dose of 50 x 10⁶ MSCs intranasally. We will use a sterile plastic (e.g. 1,0 mL) syringe containing the MSCs to slowly drip the MSCs alternatively in both nostrils.

24 hours after MSC administration, blood samples will be collected again. Blood samples are taken routinely in the hospital for clinical purposes, but some extra material (0.5-1 mL) will be collected to determine infection markers CRP, procalcitonin and complete blood count. These samples will be combined with routine blood sampling and taken from routinely placed (arterial) catheters.

During their stay on the NICU, vital functions of the infant will be monitored, as part of standard clinical care. Cranial ultrasound and neurologic examination will be performed as part of standard clinical care for neonates with PAIS. These procedures will at least all be performed before and 24 hours after MSC treatment, until discharge from the NICU.

All subjects will remain on the NICU of the study center during treatment and for at least 4 days after intervention to monitor acute safety. However, if a subject is transferred to a level II or level I neonatal unit at another hospital during the intervention period, the protocol will be continued under supervision of the principal investigator (PI) and delegated staff.

Safety monitoring

All potential risks are described in chapter 11.1e. These can be summarized in five categories: administration reactions; bacteraemia; systemic infections; post-administration viral infections and ectopic tissue formation. For all infants, these risks will be closely monitored and planned actions are described in chapter 11.2. Additionally, all infants will be monitored more closely by (extra) blood sampling, meaning blood sampling before and 24

hours after MSC administration. Also, we will only continue this study after the first three infants had their second MRI (at three months of age) to assess the size of the infarction and other brain abnormalities on MRI (at three months of age), see paragraph 6.7.

AEs and SAEs occurring during the study will be recorded in the manner described under Section 7.2. All SAEs will be followed up until resolution or until the event is considered stable. SAEs resulting in a life threatening condition or death will be reported to the regulatory authorities and the EC in line with the local regulatory requirements. In addition the investigator will report any SAEs resulting in death and/or a life-threatening situation and any unexpected related SAEs to the regulatory authorities and the Ethics Committee (EC) in line with the local regulatory requirements. An independent data safety and monitoring board (DSMB) has, in addition to an internal safety review committee, been established to carry out further safety surveillance (see Paragraphs 7.2.3 and 7.4).

[figure not shown]
MRI measurements

For secondary parameters, subjects will be scanned on a 3 Tesla MR scanner as soon as possible after clinical suspicion of PAIS and again 3 months after the MSC treatment. Further details on MRI measurements can be found in chapter 6. All infants will return to the WKZ, UMCU for a MRI scan at 3 months of age.

Follow-up

After the intervention period, subjects will be followed until 3 months corrected age. At 3 months neurological assessment will be performed as part of the regular stroke follow-up program. This will also include filming spontaneous and endogenous movements (General Movements). Additionally, fidgety movements will be assessed. Neuromotor development will also be assessed using the HINE. After parental consent, results from these examinations will be used for this study. Subjects in this study will also be followed for at least 2 years of age at regular time points. This follow-up is part of regular care for neonates with PAIS, but these results are not part of this study protocol and are beyond the scope of this study.

